### Dose Delay and Toxicity Management

ONLY if any of the following criteria are met and the event cannot be ascribed to lenalidomide, carfilzomib, dexamethasone, or underlying MM, the isatuximab infusion must be held to allow for recovery from toxicity. The criteria for a dose delay are:

- Grade 4 hematologic toxicity (except for Grade 4 lymphopenia), or Grade 3 or higher thrombocytopenia with bleeding.
- Febrile neutropenia of any grade.
- Neutropenia with infection, of any grade.
- Grade 3 or higher nonhematologic toxicities with the following exceptions:
  - Grade 3 nausea or Grade 3 vomiting that responds to antiemetic treatment.
  - Grade 3 diarrhea that responds to antidiarrheal treatment.
  - Grade 3 fatigue or asthenia that was present at baseline and lasts for <7 days after the last administration of isatuximab.
  - Grade 3 or 4 electrolyte disturbances which can be managed with replacement therapy.

If isatuximab administration does not commence within the prespecified window (Table 8) of the scheduled administration date, then the dose will be considered a missed dose. Administration may resume at the next planned dosing date.

The maximum delay for toxicity before treatment is permanently discontinued will be 3 weeks; however, delays due to other circumstances should be discussed with the Principal Investigator. Delays of >3 weeks must be discussed with the Principal Investigator. Re-treatment will be at the discretion of the Principal Investigator.

**Table 8: Isatuximab-Related Toxicity Management**

Cycles	Frequency	Missed Dose	Dosing Resumption
1-2	Weekly (every 1 week)	>3 days	Next planned weekly dosing date
3-6	Every cycle (every 2 weeks)	>14 days	Next planned every 2 weeks dosing date
7 and beyond	Every cycle (every 4 weeks)	>28 days	Next planned every 4 weeks dosing date

A missed dose will not be made up. Any AE deemed to be related to isatuximab that requires a

dose hold of more than 28 days in the induction or consolidation phase will result in permanent discontinuation of isatuximab.

### **Interruption or Missed Doses**

An isatuximab dose held for more than 8 days during induction or 14 days during maintenance from the per-protocol administration date for any reason other than toxicities suspected to be related to isatuximab should be brought to the attention of the sponsor at the earliest possible time. Subjects who miss  $\geq 3$  consecutive planned doses of isatuximab for reasons other than toxicity will be withdrawn from treatment, unless, upon consultation with the sponsor and the review of safety and efficacy, continuation is agreed upon.

### **Carfilzomib and Lenalidomide Dose Modification Guidelines**

Dose adjustments of lenalidomide will follow the approved labeling as follows:

- Starting dose: 25 mg
- Dose level -1: 15 mg
- Dose level -2: 10 mg
- Dose level -3: 5 mg

Dose adjustments should be based on the highest grade of toxicity that is ascribed to lenalidomide.

Dose adjustments of carfilzomib as follows:

- Starting dose: 56 mg/m^2 (Cycle 1 Day 1: 20 mg/m^2)
- Dose level -1: 45 mg/m^2
- Dose level -2: 36 mg/m^2
- Dose level -3: 27 mg/m^2

The maximum delay for toxicity before treatment is permanently discontinued will be 3 weeks; however, delays due to other circumstances should be discussed with the Principal Investigator. Delays of >3 weeks must be discussed with the Principal Investigator. Re-treatment will be at the discretion of the Principal Investigator.

If either the lenalidomide or carfilzomib dose level is reduced during a given cycle, the reduced dose level will be continued for the next cycle. If the reduced dose level is tolerated for a complete cycle, the subject may, at the investigator's discretion, resume the dose level prior to the reduction at the start of the subsequent cycle.

**Table 9 – Lenalidomide and Carfilzomib Dose Modifications**

	Recommended Actions	
Thrombocytopenia	Lenalidomide	Carfilzomib

Return to $\geq 30 \times 10^9/L$	Resume lenalidomide at full dose	Resume carfilzomib at full dose.
Subsequently drop to $< 30 \times 10^9/L$	Hold lenalidomide and follow CBC weekly	Hold carfilzomib and follow CBC weekly
Return to $\geq 30 \times 10^9/L$	Resume lenalidomide at 1 dose decrement	Resume carfilzomib at one dose decrement if cyclical thrombocytopenia is still below levels considered safe by the Treating Investigator at one dose decrement (i.e., dose decrease only if Treating Investigator judgment is that Carfilzomib contributed to thrombocytopenia)

**Platelet transfusions should also be considered for the management of thrombocytopenia as clinically indicated**

	Recommended Action	
Neutropenia : When ANC	Lenalidomide	Carfilzomib
Falls to $< 0.5 \times 10^9/L$ or to $< 1.0 \times 10^9/L$ with fever	Hold lenalidomide, add filgrastim if Grade 3 with fever or Grade 4, follow CBC weekly	Hold carfilzomib, add filgrastim if Grade 3 with fever or Grade 4, follow CBC weekly
Returns to $1.0 \times 10^9/L$ (if neutropenia was the only toxicity noted)	Resume lenalidomide at full dose	Resume carfilzomib at full dose
Return to $1.0 \times 10^9/L$ (if other toxicity noted)	Resume lenalidomide at 1 dose decrement	Resume carfilzomib at full dose unless marked cyclical thrombocytopenia is present, then reduce by 1 dose decrement
Subsequently drops to $< 0.5 \times 10^9/L$ or to $< 1.0 \times 10^9/L$ with fever	Hold lenalidomide treatments	Hold carfilzomib treatments
Returns to $1.0 \times 10^9/L$	Resume lenalidomide at 1 dose decrement	Resume carfilzomib previous dose at 1 dose decrement (dose decrease required only if treating investigator judgment is that Carfilzomib contributed to neutropenia)

Absolute neutrophil count (ANC); Complete blood count (CBC)

Toxicity	Recommended Action	
	Lenalidomide	Carfilzomib
Non-Blistering Rash		
Grade 3	Hold lenalidomide dose; follow weekly If the toxicity resolves to $\leq$ Grade 1 prior to Day 21 of the current cycle, restart at 1 dose decrement and continue the cycle until Day 21 of the current cycle.	Hold (if Treating Investigator's opinion is possibly related to Carfilzomib) until $\leq$ Grade 1, reinstitute at current dose
Grade 4	Discontinue lenalidomide study drug.	Hold until $\leq$ Grade 1, reinstitute at current dose.
Desquamating (blistering) rash – any grade	Discontinue lenalidomide study drug.	Hold until $\leq$ Grade 1, reinstitute at current dose.
Erythema multiforme <math>\geq</math> Grade 3	Discontinue lenalidomide study drug.	Hold until $\leq$ Grade 1, reinstitute at current dose.
Sinus bradycardia/ other cardiac arrhythmia		
Grade 2	Hold lenalidomide dose. Follow at least weekly. If the toxicity resolves to $\leq$ Grade 1 prior to Day 21, restart at 1 dose decrement and continue the cycle until Day 21.	Hold until $\leq$ Grade 1, reinstitute at current dose.
$\geq$ Grade 3	Discontinue lenalidomide study drug	Hold until $\leq$ Grade 1, reinstitute at current dose.
Allergic reaction/hypersensitivity		
Grade 2 – 3	Hold lenalidomide dose. Follow at least weekly. If the toxicity resolves to $\leq$ Grade 1 prior to Day 21, restart at 1 dose decrement and continue the cycle until Day 21.	Hold until $\leq$ Grade 1, reinstitute at current dose.
Grade 4	Discontinue	Discontinue

Toxicity	Recommended Action	
	Lenalidomide	Carfilzomib
Tumor lysis syndrome (≥ 3 of the following: ≥ 50% increase in creatinine, uric acid, or phosphate; ≥ 30% increase in potassium; ≥ 20% decrease in calcium; or ≥ 2-fold increase in LDH)	Hold lenalidomide until all abnormalities in serum chemistries have resolved. Reinstitute at full doses.	Hold carfilzomib until all abnormalities in serum chemistries have resolved. Reinstitute at full doses.
Infection Grade 3 or 4	Hold lenalidomide until systemic treatment for infection is completed. If no neutropenia, restart both drugs at full dose. If neutropenic, follow neutropenic instructions.	Hold carfilzomib until systemic treatment for infection is completed. If no neutropenia, restart both drugs at full dose. If neutropenic, follow neutropenic instructions.
Herpes zoster or simplex of any grade	Hold lenalidomide until lesions are dry. Reinstitute at full doses.	Hold carfilzomib until lesions are dry. Reinstitute at full doses.
Grade 2 neuropathy with pain or any Grade 3 neuropathy	Hold until ≤ Grade 2. Then restart lenalidomide at 1 dose decrement	Hold until resolved to ≤ Grade 2. Then restart carfilzomib at 1 dose decrement
Grade 4 neuropathy	Discontinue	Discontinue
Toxicity	Recommended Action	
	Lenalidomide	Carfilzomib
Renal dysfunction		
Serum creatinine > 2 mg/dL	Base dose reduction on calculated GFR (below)	Base dose reduction on calculated GFR (below)
CrCl > 50 mL/min	Full dose	Full dose
CrCl < 50 mL/min > 30 mL/min	Reduce lenalidomide to 10 mg every 24 h; may reinstate prior dose if, after 2 cycles, CrCl normalizes	Full dose

CrCl < 30 mL/min	Reduce lenalidomide to 15 mg every 48 h	Hold carfilzomib until CrCl > 30 mL/min; restart at 1 dose decrement
CrCl < 30 mL/min requiring dialysis	5 mg. Once daily. On dialysis days the dose should be administered following dialysis.	Hold until resolved to ≤ Grade 2. Then restart carfilzomib at 1 dose decrement
Venous thrombosis/embolism ≥ Grade 3	Hold lenalidomide dose and adjust anticoagulation regimen; re-start at Treating Investigator's discretion at full dose	No adjustment required
Hyperthyroidism or hypothyroidism	Omit lenalidomide for remainder of cycle, evaluate, and initiate appropriate therapy. Restart lenalidomide next cycle at 1 dose decrement	No adjustment required
Congestive heart failure (CHF)	Any subject with symptoms of CHF, whether or not lenalidomide related, must have the dose held until resolution or return to baseline. If CHF was felt to be lenalidomide related, reinstate by one dose decrement after return to baseline. If no resolution of CHF after 2 weeks, the subject will be withdrawn from the study.	Any subject with symptoms of CHF, whether or not carfilzomib related, must have the dose held until resolution or return to baseline. If CHF was felt to be carfilzomib related, reinstate by one dose decrement after return to baseline. If no resolution of CHF after 2 weeks, the subject will be withdrawn from the study.
Hypertension including Hypertensive Crises	NA	≥ Grade 3: Carfilzomib attribution, hold drug until resolved to ≤ Grade 2. Resume at one level dose reduction
Toxicity	Recommended Action	
	Lenalidomide	Carfilzomib

Heart problems, including rapid, strong, or irregular heartbeat
 
Heart attack, reduced blood flow to the heart, abnormal amount of fluid between the heart and lining around the heart, and swelling/irritation of the lining around the heart
	
NA
	
≥ Grade 3: Carfilzomib attribution, hold drug until resolved to ≤ Grade 1. Resume at one level dose reduction

Pericardial Effusion
	
NA
	
≥ Grade 3: Carfilzomib attribution, hold drug until resolved to Grade 1. Resume at one level dose reduction

Pericarditis
	
NA
	
≥ Grade 3: Carfilzomib attribution, hold drug until resolved to Grade 1. Resume at one level dose reduction

Toxicity
	
Recommended Action
	
	
Lenalidomide
	
Carfilzomib

Pulmonary Hypertension
	
NA
	
= Grade 2: Carfilzomib attribution, Reduce drug: one level dose reduction
 
≥ Grade 3: Carfilzomib attribution, hold drug until resolved to ≤Grade 2. Resume at one level dose reduction


Pulmonary Toxicities: Interstitial Lung Disease (inc. pneumonitis), Acute Respiratory Failure, and Adult Respiratory Distress Syndrome (ARDS), cough and cough with phlegm
	
NA
	
≥ Grade 2 for Pneumonitis ≥ Grade 3 for ARDS ≥ Grade 4 for Respiratory Failure
 
Carfilzomib attribution, hold drug until resolved to ≤Grade 1. Resume at one level dose reduction

Blood clot in the lungs, fluid in the lungs, bleeding in the lungs
	
NA
	
≥ Grade 3: Carfilzomib attribution, hold drug until resolved to ≤ Grade 1. Resume at one level dose reduction

Gastrointestinal Perforation
	
NA
	
≥ Grade 3: Carfilzomib attribution, hold drug until resolved to Grade 1. Resume at one level dose reduction

Hepatic Toxicities (<math>\geq</math> Grade 3 elevation of AST or ALT, Bilirubin, or other <math>\geq</math> Grade 3 liver abnormalities)	Hold drug until resolved to $\leq$ Grade 1 or baseline. Resume at the same dose or reduced dose as appropriate. If tolerated, the reduced dose may be escalated to the previous dose at the discretion of the physician. Frequent monitoring of liver function should then be implemented.	Hold drug until resolved to $\leq$ Grade 1 or baseline. Resume at the same dose or reduced dose as appropriate. If tolerated, the reduced dose may be escalated to the previous dose at the discretion of the physician. Frequent monitoring of liver function should then be implemented. Please see additional information on hepatic impairment in Table 9
Other non-hematologic toxicity assessed as lenalidomide-related <math>\geq</math> Grade 3	Hold lenalidomide dose. Follow at least weekly. If the toxicity $\leq$ Grade 1 before Day 21 of the current cycle, restart at 1 dose decrement and continue until Day 21 of the current cycle	Full dose
Other non-hematologic toxicity assessed as carfilzomib-related	Full dose	Hold carfilzomib dose until toxicity resolves to $\leq$ Grade 1 or baseline. Restart at 1 dose decrement
Other non-hematologic toxicity assessed as drug-related <math>\geq</math> Grade 3	Hold treatment and restart at 1 dose decrement when toxicity has resolved to $\leq$ Grade 1 or baseline	Hold treatment and restart at 1 dose decrement when toxicity has resolved to $\leq$ Grade 1 or baseline

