## 5.2 Pre-Treatment Criteria

A new cycle of treatment may begin on the scheduled Day 1 of a new cycle if the following criteria are met within 24 hours of Day 1:

- ANC  $\geq 1,000/\text{mm}^3$  (growth factor support is permitted during cycles with the exception of Cycle 1 Day 1 (C1D1); it is allowed on the same day as treatment administration).
- Platelet count  $\geq 50,000/\text{mm}^3$  (platelet support is permitted during cycles of treatment; it is allowed on the same day as treatment administration, including C1D1).
- Any lenalidomide-related allergic reaction/hypersensitivity or sinus bradycardia/other cardiac arrhythmia AE that may have occurred has resolved to < Grade 1.
- Any other lenalidomide, carfilzomib, or isatuximab-related adverse event that may have occurred has resolved to <Grade 2.
- Herpes zoster lesions, if present, are dry.

If these conditions are not met on Day 1 of a new cycle, the subject will be evaluated weekly and a new cycle of therapy will not be initiated until the toxicity has resolved as described above. The maximum amount of time that treatment may be held for these toxicities to resolve is 3 weeks. If drug is held for more than 3 weeks due to toxicity, the patient is to discontinue all study treatment and enter the survival follow-up phase of the study.

For intra-cycle dosing on days where laboratory studies are scheduled, the following criteria must be met:

- Platelet count  $\geq 30,000$  (platelet transfusion support is permitted to meet criteria)
- Absolute neutrophil  $\geq 500/\text{mm}^3$  (growth factor support is permitted during cycles with the exception of Cycle 1 Day 1 (C1D1); it is allowed on the same day as treatment administration).

Intra-cycle dose modifications for all drugs will be allowed based on toxicity and according to dose modifications outline in Section 6.1, Table 9.

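### Table 9 releases the neuropathy hold at Grade 2 or less without mentioning pain, so painful Grade 2, itself a hold trigger, already meets the release

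*Combined protocol and SAP*

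**What the plan says.** One row of Table 9 in section 6.1 covers "Grade 2 neuropathy with pain or any Grade 3 neuropathy". The lenalidomide cell reads "Hold until ≤ Grade 2. Then restart lenalidomide at 1 dose decrement" and the carfilzomib cell reads "Hold until resolved to ≤ Grade 2. Then restart carfilzomib at 1 dose decrement". The next row stops both drugs for Grade 4 neuropathy. No other section gives a release rule specific to neuropathy.

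Section 5.2 sets the conditions for starting a new cycle. On Day 1, any other lenalidomide-, carfilzomib- or "isatuximab-related adverse event that may have occurred has resolved to <Grade 2". Dosing inside a cycle has its own list, introduced by "For intra-cycle dosing on days where laboratory studies are scheduled, the following criteria must be met"; that list contains only platelets and neutrophils. For everything else the section says "Intra-cycle dose modifications for all drugs will be allowed based on toxicity and according to dose modifications outline in Section 6.1, Table 9".

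**The concern.** A hold needs a release that the triggering state does not already satisfy. Here pain is what turns Grade 2 neuropathy into a hold trigger, yet pain is absent from the release. The grade alone cannot end the hold sensibly, because painful Grade 2 and painless Grade 2 carry the same grade.

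The likely intent is to hold until the pain clears: the trigger specifies pain, and the carfilzomib cell speaks of resolution. Neither cell says so, and the lenalidomide cell lacks even the reference to resolution. Two investigators could read the row in good faith and act differently, one continuing both drugs a level lower and the other holding them. What is at stake is continued exposure within a cycle for a patient with painful neuropathy.

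**Working it through.** The core of this check is logical; the plan states no figure to reproduce.

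**The row against itself**

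| Starting state | Held? | Meets Grade 2 or less? | Result as written |
|---|---|---|---|
| Grade 2 with pain | Yes | Yes, at onset | Hold has no length; only the decrement remains |
| Grade 3, easing to Grade 2 with pain | Yes | Yes, once at Grade 2 | Restart in a state the row lists as a trigger |
| Grade 3, easing to Grade 2 without pain | Yes | Yes | Restart, with no contradiction |

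The first two lines apply to both drugs.

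**Other rows of Table 9.** The other holds that name Grade 2 as a trigger release at Grade 1 or less. For Grade 2 arrhythmia, lenalidomide restarts if the event resolves to at most "Grade 1 prior to Day 21, restart at 1 dose decrement and continue the cycle until Day 21". The allergic-reaction row (Grades 2 to 3) uses the same release. For pneumonitis of Grade 2 or higher, the carfilzomib instruction is "hold drug until resolved to ≤Grade 1. Resume at one level dose reduction". Release grades vary across the table, so this comparison supports the point but does not prove a drafting error.

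**Section 5.2.** The below-Grade-2 condition applies on Day 1 only. On later dosing days the listed criteria are blood counts, and the section points back to Table 9. The gap therefore stays open from Day 2 to the end of the cycle.

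**Largest exposure in one cycle.** Inputs are the dose levels in section 6.1 (lenalidomide 25, 15, 10, 5 mg; carfilzomib 56, 45, 36, 27 mg/m²) and the schedules in section 5.1. One decrement is (25 − 15)/25 = 40% for lenalidomide and (56 − 45)/56 = 19.6% for carfilzomib.

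Induction carfilzomib (Days 1, 8, 15):
- Painful Grade 2 present on Day 1 is stopped by section 5.2.
- Onset on Days 2 to 8 leaves 2 doses, onset on Days 9 to 15 leaves 1, and later onset leaves 0.
- Two doses at full level: 2 × 56 = 112 mg/m².
- Row applied once: 2 × 45 = 90 mg/m² (80% of full).
- Row applied again on Day 15 because the pain persists: 45 + 36 = 81 mg/m² (72% of full).
- Drug held and pain not clearing: 0.

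Induction lenalidomide (Days 1 to 21): onset on Day 2 leaves Days 2 to 21, which is 20 doses. That gives 20 × 15 = 300 mg, against 20 × 25 = 500 mg at full dose and 0 if held. The 300 mg is an upper bound, since applying the row again would lower it.

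Maintenance: in high-risk patients (carfilzomib Days 1 and 15) one dose remains, 45 mg/m². Lenalidomide is 10 mg in both risk groups. Taking the next listed level, 5 mg, as the decrement gives 20 × 5 = 100 mg, against 200 mg at full dose.

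**Number of patients.** This cannot be derived. The nearest figure, in section 2.3, is 36% peripheral neuropathy with isatuximab plus carfilzomib in relapsed disease. It does not separate painful Grade 2. The same paragraph reports fewer than 5% of the listed events at Grade 3 or 4, and no dose reduction of either drug. Patients with neuropathy of Grade 2 or higher at screening are excluded (section 3.2).

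**The case against.** The strongest reply is that the literal reading defeats itself. If painful Grade 2 satisfies the release, the instruction to hold does nothing for the first trigger. A sensible reader would hold until the trigger is no longer met, and the row may in any case apply again at the next dose. On this view only a clarification of wording is needed.

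Further points reduce the weight:
- The Table 9 columns are headed as recommended actions, and section 6.1 (Treatment Discontinuation) lets the Treating Investigator stop any drug permanently for treatment-related toxicity. Nothing compels redosing.
- Continuing one level lower at Grade 2 is not foreign to the table: Grade 2 pulmonary hypertension calls for a carfilzomib reduction without a hold.
- In the arrhythmia and allergic-reaction rows the stricter release goes with carfilzomib restarting at its current dose, whereas the neuropathy row reduces both drugs.
- Release at Grade 2 or less after a Grade 3 event appears elsewhere (hypertension, pulmonary hypertension, other lenalidomide-related Grade 3 or 4 events), so for the Grade 3 trigger only the missing pain condition is at issue.

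These points stand as limits on size. They do not supply the missing release condition. The pulmonary hypertension row cuts the other way: where the table wants a reduction without a hold, it says *reduce*, while the neuropathy row says *hold*. The discretion to stop a drug permanently does not say when a temporary hold ends.

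**Conclusion.** The point holds. As written, the release is met by a state that the same row lists as a trigger, for both triggers and both drugs, and section 5.2 does not correct this within a cycle. It is a minor safety correction that should be made. Per patient and cycle, the literal reading permits at most 2 reduced carfilzomib doses (81 to 90 mg/m²) and 20 reduced lenalidomide doses (up to 300 mg) in induction, and less in maintenance.

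These figures assume that the patient starts from full dose, that the neuropathy counts as drug-related so the Day 1 check applies, and that the painful state lasts to the end of the cycle. The decrement, the Day 1 check and investigator discretion remain as protection. How often this would occur is unknown, and no effect on the primary endpoint is claimed.

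**What to change.** Keep one row. In both columns and for both triggers, replace the release with: *Hold until Grade 1 or less, or Grade 2 without pain, then restart at 1 dose decrement.* Add: *Section 5.2 still requires below Grade 2 before Day 1 of a new cycle.* This is the most lenient release consistent with the row's own trigger. Using it for both triggers avoids a stricter rule for the milder event and prevents a Grade 3 event from restarting at painful Grade 2.

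The edit is two cells plus one sentence. The cost is a somewhat longer hold within a cycle for a few patients, some of whom could reach the 3-week limit. The consequences there differ by section. Section 5.2 stops all study treatment once toxicity has kept drug on hold beyond 3 weeks; section 6.1 leaves re-treatment to the Principal Investigator. Under Treatment Discontinuation in section 6.1, permanently stopping one of the three main drugs before Cycle 4 ends treatment at the close of Cycle 4 induction. A full stop before Cycle 4 could also cost that patient the 4-cycle response assessment. Nothing is added on Day 1, where section 5.2 is already stricter.

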**Maintenance:**

Patients must achieve a PR or better to continue onto maintenance therapy on the study.

28-day Maintenance Cycle until progressive disease (PD) or unacceptable toxicity. Subjects will be stratified based on cytogenetics (deletion (del) 17, translocation (t)(4:14), t(14;16), t(14;20), 1q duplication).

Standard-risk:

Lenalidomide 10 mg po Days 1-21

High-risk:

Carfilzomib 56 mg/m^2 (or last tolerated dose) IV Days 1, 15

Lenalidomide 10 mg po Days 1-21

Isatuximab 10 mg/kg IV Day 1 for up to 24 cycles of maintenance (two years), then discontinue

In the maintenance phase, dexamethasone, 20 mg orally or IV will be administered to subjects as a preinfusion medication prior to isatuximab dosing. When dexamethasone is reduced to 20 mg/week and is given as preinfusion medication, subjects may receive low-dose methylprednisolone ( $\leq 20$  mg) orally (or equivalent in accordance with local standards) for the prevention of delayed infusion-associated reactions (IARs), as clinically indicated.

Because lenalidomide is primarily excreted unchanged by the kidney, adjustments to the starting dose of lenalidomide are recommended to provide appropriate drug exposure in patients with renal impairment. Lenalidomide dose adjustment should be instituted for patients with a CrCl  $\leq 50$  mL/min. The recommended doses for patients with multiple myeloma and renal impairment are shown below in Table 9. If during treatment a patient's renal status changes, the dose should be adjusted as shown in Table 9. Similarly, adjustments to the starting and ongoing dosing of carfilzomib are recommended in the setting of hepatic impairment. The doses should be adjusted as shown in Table 10.

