### **5.3.3.5 Treatment Schedule and Administration**

During the induction phase of treatment, lenalidomide will be self-administered at a dose of 25 mg orally each day on Days 1 through 21 of each 28-day cycle for subjects with creatinine clearance (CrCl) >50 mL/min. During the maintenance phase for all patients, lenalidomide 10 mg will be administered daily on days 1-21 throughout each 28-day cycle until progressive disease (PD) or unacceptable toxicity.

Lenalidomide should be taken orally at about the same time each day. The capsules should not be opened, broken, or chewed. Lenalidomide capsules should be swallowed whole, preferably with water, either with or without food.

If less than 12 hours has elapsed since missing a dose, the patient can take the dose. If more than 12 hours has elapsed since missing a dose at the normal time, the patient should not take the dose, but take the next dose at the normal time on the following day. Do not take 2 doses at the same time.

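### Maintenance lenalidomide is 10 mg for all patients, which conflicts with the rule that carries a reduced dose forward, and the fixed renal doses in Table 9 do not fit the maintenance phase

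*Combined protocol and SAP*

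**What the plan says.** **Induction and maintenance doses.** Section 5.3.3.5 ties the induction dose to renal function: "25 mg orally each day on Days 1 through 21 of each 28-day cycle for subjects with creatinine clearance (CrCl) >50 mL/min". The next sentence sets maintenance without a renal condition: "During the maintenance phase for all patients, lenalidomide 10 mg will be administered daily on days 1-21 throughout each 28-day cycle". The Maintenance part of Section 5.1 lists the same 10 mg for standard-risk and high-risk patients. Carfilzomib maintenance (Sections 5.1 and 5.3.2.6) may be given at the last tolerated dose. Lenalidomide has no matching clause.

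**Dose levels.** Section 6.1 gives one lenalidomide ladder, beginning "Starting dose: 25 mg" and stepping down to 15, 10 and 5 mg. When a level is reduced during a cycle, "the reduced dose level will be continued for the next cycle". The earlier level may be resumed after a complete tolerated cycle, if the investigator so decides. The paragraph is not limited to one phase.

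**Renal rules.** The Maintenance part of Section 5.1 asks for an adjustment at CrCl of 50 mL/min or below and adds: "If during treatment a patient's renal status changes, the dose should be adjusted as shown in Table 9". Table 9 then gives fixed doses:
- CrCl 30–50: "Reduce lenalidomide to 10 mg every 24 h; may reinstate prior dose if, after 2 cycles, CrCl normalizes"
- CrCl below 30: "Reduce lenalidomide to 15 mg every 48 h"
- CrCl below 30 on dialysis: "5 mg. Once daily. On dialysis days the dose should be administered following dialysis"

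Most other lenalidomide rows of Table 9 that cut the dose use a relative step of one decrement.

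**The concern.** There are two linked problems.

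First, two sections give different doses to the same patient. Someone reduced to 5 mg by the end of induction or consolidation is placed on 10 mg by the maintenance schedule but held at 5 mg by the carry-forward rule. The text does not say which prevails.

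Second, the ladder and the renal rows are anchored to 25 mg but also apply at a maintenance dose of 10 mg. A row worded as a reduction can then leave the dose where it is or, for a patient already below 10 mg, name a higher one. Section 5.1 explains that the adjustment exists because lenalidomide is cleared by the kidney, so a rule that cannot act in one phase deserves attention.

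The situation is foreseeable. Eligibility admits CrCl from 30 mL/min (Section 3.1), CrCl is measured in maintenance (Tables 14A and 14B), and lenalidomide is the only scheduled maintenance drug for standard-risk patients. At stake are patient safety and consistent dosing in a phase that continues until progression or intolerance.

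**Working it through.** The plan states no figure to reproduce here, so the check is dose arithmetic.

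**Inputs.** 25 mg and 10 mg, Days 1–21 (Section 5.3.3.5); levels 15, 10 and 5 mg (Section 6.1); renal doses of 10 mg every 24 h, 15 mg every 48 h and 5 mg daily (Table 9).

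**Formulas.** Cycle total = dose × number of dosing days. Mean daily dose = dose ÷ interval in days. Change = new ÷ current − 1.

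**Cycle totals over Days 1–21.**
- 25 mg daily: 25 × 21 = 525 mg
- 10 mg daily: 10 × 21 = 210 mg
- 5 mg daily: 5 × 21 = 105 mg
- 15 mg every 48 h: Days 1, 3, …, 21 is 11 doses; 11 × 15 = 165 mg; mean 15 ÷ 2 = 7.5 mg/day

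Table 9 does not say whether its renal doses keep the Days 1–21 limit. Every 48 h for all 28 days would be 14 × 15 = 210 mg.

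**Step 1: maintenance entry.** From 5 mg to 10 mg: 210/105 − 1 = +100% under Section 5.3.3.5, and 0% under the carry-forward rule of Section 6.1. The conflict is sharpest when the cut falls in the last cycle before maintenance, because the reduced level must then be continued. If 5 mg has already been tolerated for a full cycle, Section 6.1 makes the return discretionary, while Section 5.3.3.5 makes 10 mg automatic. Patients at 25 or 15 mg go down at entry, and those at 10 mg are unchanged, so the conflict concerns doses below 10 mg.

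**Step 2: renal rows by current dose (Days 1–21).**

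| Current dose | CrCl 30–50 row | CrCl <30 row | Dialysis row |
|---|---|---|---|
| 25 mg (525 mg) | 210/525 − 1 = −60% | 165/525 − 1 = −69% | 105/525 − 1 = −80% |
| 10 mg (210 mg) | 210/210 − 1 = 0% | 165/210 − 1 = −21% | 105/210 − 1 = −50% |
| 5 mg (105 mg) | 210/105 − 1 = +100% | 165/105 − 1 = +57% | 0% |

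From 10 mg, the CrCl <30 row gives 210/210 − 1 = 0% if run for 28 days. In mean daily dose it is 7.5/10 − 1 = −25%, although each single dose rises from 10 to 15 mg. From 5 mg, the same row is 7.5/5 − 1 = +50% in mean daily dose.

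**Step 3: non-renal rows.** One decrement from 10 mg is 5 mg, or −50%. These rows work in maintenance, although no level is defined below 5 mg.

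**The case against.** The strongest reply is that little of this is a contradiction.

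- Table 9 names 10 mg as the dose for CrCl 30–50. A maintenance patient in that band already takes it, and nothing in the documents promises a percentage cut from every starting dose.
- The row says to reduce, and the table presents its entries as recommendations. Reading it as an order to double a 5 mg dose goes against its own verb.
- The reference to all patients in Section 5.3.3.5 may mean both risk groups, since the carfilzomib and isatuximab maintenance text is for high-risk patients only.
- The carry-forward conflict needs a patient at the lowest ladder step, whose prior level may well be 10 mg.

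Much of this stands as a limit on size. Whether 10 mg is a suitable dose at CrCl 30–50 is a clinical judgement outside this review. It remains that Section 5.1 calls for an adjustment in that band within the maintenance text and the row it points to makes none. It also remains that no sentence settles what happens to a dose already below 10 mg, and a reader who relies on the verb has to set aside the number printed beside it.

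Three stronger readings are tempting but not supported:
- **That the renal rows raise the dose in maintenance generally.** From 10 mg the changes are 0%, −21% (or 0% over 28 days) and −50%. A rise appears only from 5 mg, or if level −1 (15 mg) is misread as the first step down from 10 mg.
- **That a patient on 15 mg every 48 h is necessarily raised at maintenance entry** (210/165 − 1 = +27%). This requires Section 5.3.3.5 to override Section 5.1, which can be read as keeping Table 9 in force.
- **That PFS is affected.** The documents give no basis for a size, or for the number of patients concerned.

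**Conclusion.** The point holds in a limited form. Sections 5.3.3.5 and 6.1 give different lenalidomide doses (10 mg against 5 mg, a difference of 100%) to a patient entering maintenance after reduction to 5 mg, and the last-tolerated-dose clause that exists for carfilzomib is missing. The CrCl 30–50 row has no effect from the maintenance dose. Taken literally, that row and the CrCl <30 row are increases from 5 mg (+100%, and +57% per cycle or +50% in mean daily dose).

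The percentages assume that the renal doses keep the Days 1–21 schedule unless stated otherwise. The frequency of affected patients is unknown.

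The primary endpoint, CR after 4 cycles, precedes maintenance and is untouched. The conflict still needs correcting before sites apply it, because following the protocol as written can yield contradictory doses with a possible safety consequence.

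**What to change.** Reconcile Section 5.1 (Maintenance), Section 5.3.3.5, the dose-level paragraph of Section 6.1 and the renal rows of Table 9, so that:
- each lenalidomide rule states the phase and the current dose it applies to, including what full dose and prior dose mean in maintenance;
- the text states whether a dose reduced for toxicity, or adjusted for renal function, carries into maintenance;
- the renal rows state the dosing days they assume.

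The sponsor sets the doses; none is proposed here.

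The cost is a short text amendment. No visits or tests are added, since CrCl is already measured in maintenance, and the sample size and primary analysis do not change.
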